10. STATISTICAL DESIGN

A Statistical Analysis Plan (SAP) will be written and finalized prior to database lock. The following is a brief description of the analyses to be described in this plan.

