8. STUDY DESIGN

8.1 Study Design

This study is a prospective, multi-center, non-randomized, non-blinded follow-up study to evaluate the use of CORI Robotics in UKA and TKA procedures in achieving post-operative leg alignment. Up to 8 sites will participate within Europe, UK, India and the US.

Subjects will be enrolled in one of two (2) groups based on medical indication and general practice at the site, as shown in Table 8-1. All subjects are treated with knee arthroplasty with the use of the CORI Robotics and a Smith+Nephew Knee Implant System based local regulatory status and medical indication and general practice at the site (see Table 6-1 S+N Implant Systems available with CORI Robotics for this study).

Table 8-1 Overview of Study Groups

Group	Surgical Technique	Knee Implant system	Number of Subjects
Primary UKA	CORI Robotics	Smith+Nephew UKA Implant System	40
Primary TKA	CORI Robotics	Smith+Nephew TKA Implant System	40

The study is expected to enroll all subjects within a 24 month timeframe. Subjects will be followed-up for a time period of 12 months after surgery.

This study is being conducted in parallel to 2 randomized-controlled studies in China titled: "A Prospective, Multi-center, randomized-controlled Study to Evaluate the Safety and Effectiveness of REAL INTELLIGENCE™ CORI™ in unicondylar knee arthroplasty (UKA) procedure" (Protocol ID: CORI.2019.06) and "A Prospective, Multi-center, Randomized Controlled Study to Evaluate the Safety and Effectiveness of the REAL INTELLIGENCE™ CORI™ in total knee arthroplasty (TKA) Procedure" (Protocol ID: CORI.2020.08). The study data may be combined for analysis to meet the requirements for regulatory approval of the CORI Robotics by the National Medical Products Administration (NMPA) in China. Further details are described in Section 10 Statistical Design and the Statistical Analysis Plan (SAP).

Figure 8-1 details the different steps of study conduct from screening to enrollment and follow-up.

Subjects may be assigned a subject ID, but then not enrolled in the study (e.g. did not receive the study device or decided not to participate in the study).

Clinical Protocol

[figure not shown]
A Prospective, Multi-center, Study to Evaluate the Safety and Effectiveness of REAL INTELLIGENCE™ CORI™ in unicondylar knee arthroplasty (UKA) and total knee arthroplasty (TKA) procedures

Study Number: CORI.2019.07

Version: 6.0, 15/Jan/2024

Page: 39 of 122

Figure 8-1 Study Flowchart

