8.3 Study Endpoints

8.3.1 Primary Endpoint

The primary endpoint of this study is defined as the evaluation of the proportion of subjects achieving post-operative leg alignment at 6 weeks post-surgery. Achieved leg alignment is defined as $\pm 3^\circ$ from the subject's specific target.

This primary endpoint is aligned to the primary study objective of evaluating the CORI surgical system for UKA and TKA procedures in achieving post-operative leg alignment. Accuracy and alignment are two key variables in successful UKA and TKA procedures. These measures have been previously evaluated with the predicate NAVIO surgical system. The primary endpoint will support the continued evaluation of these variables for the CORI surgical system.

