9.1.4 Follow-up visits at 6 weeks (42 ± 14 days)

1. Query subject regarding any changes in general health and the use of concomitant medications/therapies.
2. If any adverse device effects or device deficiencies are observed or reported, they must be recorded as instructed in Section 12 - Adverse Events and Device Deficiencies.
3. Verify with the subject if any revision has occurred since the last visit. If any revision is observed or reported, it must be recorded as instructed in Section 12 - Adverse Events and Device Deficiencies.
4. Collect the KSS score objective measures (joint alignment, instability, motions & symptoms).
5. Have the subject complete the KSS score subject questions.
6. Have the subject complete the OKS patient-reported outcome measure
7. Have the subject complete the EQ-5D-5L patient-reported outcome measure.
8. Have the subject complete the FJS patient-reported outcome measure.
9. Collect the standing weight bearing long leg (A/P) and standard lateral (non-weight bearing) radiographic images of the affected knee. Review the images to complete the appropriate eCRF for leg alignment and component alignment.

Clinical Protocol

A Prospective, Multi-center, Study to Evaluate the Safety and Effectiveness of REAL INTELLIGENCE™ CORI™ in unicondylar knee arthroplasty (UKA) and total knee arthroplasty (TKA) procedures

Study Number: CORI.2019.07

Version: 6.0, 15/Jan/2024

Page: 46 of 122

10. Instruct the subject on follow-up procedures, including returning to the site for the next follow-up visit in 6 months (185 ± 14 days) after the surgery date or make arrangements for delivery of the 6 month PROMs by courier to the subject to be completed remotely.

9.1.5 6 months (185 ± 14 days) after surgery (phone call if remote)

1. Query subject regarding any changes in general health and the use of concomitant medications/therapies.
2. If any adverse device effects or device deficiencies are observed or reported, they must be recorded as instructed in Section 12 - Adverse Events and Device Deficiencies.
3. Verify with the subject if any revision has occurred since the last visit. If any revision is observed or reported, it must be recorded as instructed in Section 12 - Adverse Events and Device Deficiencies.
4. Collect the KSS score objective measures (joint alignment, instability, motions & symptoms) (if it is an on-site visit)
5. Have the subject complete the KSS score subject questions.

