10.2 Analysis Populations

The following are the analysis populations:

- Safety Population (SAF): This is defined as all subjects who were treated for a UKA or TKA with the use of the CORI Robotics and a Smith+Nephew Knee Implant System.
- Full analysis set population (FAS): The FAS is a subset of the subjects of the SAF population who have at least one post-operative assessment on any of the effectiveness endpoints or health-related quality of life (HRQoL) endpoints.
- Per-Protocol Population (PP): The PP population is a subset of subjects in the FAS population who do not have major protocol deviations and who satisfied all enrollment eligibility criteria. Major protocol deviations will include but not only restricted to subjects enrolled who do not satisfy the study entry eligibility criteria. All other criteria that will be categorized as major deviations will be formally classified on a case-by-case basis prior to the final study database lock.

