10.4.3 Analysis of Other Endpoint(s)

The analyses for other endpoints (will be carried out separately in the CORI Robotics UKA and CORI Robotics TKA groups.

Leg alignment pre- and post-cementation

Leg alignment pre- and post-cementation will be summarized using descriptive summary characteristics for continuous variables.

Robotics System Time & Cutting Time

Robotic System and cutting times will be summarized using summary statistics for continuous variables. Standard Robotics System and cutting times will be obtained from literature and included in the SAP. The average operating (μ_{11}) and cutting times (μ_{21}) and their commensurate 95% CIs will be summarized compared to the obtained literature-specified (i.e. μ_{10} and μ_{20} respectively) using the t-test.

The following are the possible outcomes, where $i=1$ represents operating time and $i=2$ represents cutting time:

If the lower limit (LL) of the 95% CI for μ_{i1} is $> \mu_{i0}$, then it is concluded that μ_{i1} is significantly greater than μ_{i0} .

If the upper limit (UL) of the 95% CI for μ_{i1} is $> \mu_{i0}$, then it is concluded that μ_{i1} is significantly less than μ_{i0} .

If (LL of 95% CI for $\mu_{i1} \leq \mu_{i0} \leq$ UL for 95% CI of μ_{i1}), then it is concluded that μ_{i1} on-study is comparable to that specified in the literature (μ_{i0}).

All other endpoints will be summarized using the FAS analysis population.

Clinical Protocol

A Prospective, Multi-center, Study to Evaluate the Safety and Effectiveness of REAL INTELLIGENCE™ CORI™ in unicondylar knee arthroplasty (UKA) and total knee arthroplasty (TKA) procedures

Study Number: CORI.2019.07

Version: 6.0, 15/Jan/2024

Page: 59 of 122

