19. END OF STUDY

The end of this study is defined by the last follow-up visit that occurs in the whole study population. Due to defined visit windows, the last follow-up visit must not necessarily be of the last subject treated. Subject's will return to standard of care as prescribed by the individual sites if further follow-up is needed. The study is expected to last 36 months (enrolment period: 24 months, Follow-up period: 12 months).

Should circumstances arise which require the termination of the entire study prior to its planned completion (e.g., safety concerns) or circumstances arise which mean the end of the participation of an individual site (e.g., departure of Investigator, non-compliance), then this will be undertaken according to the SOPs of the Sponsor. The requirement for subject follow-up in these instances will be considered as part of these processes.

An End of Study CRF needs to be completed for all subjects including any subject that does not complete the study, to document the reason for termination.

This study may be temporarily suspended or prematurely terminated if there is sufficient reasonable cause. Written notification, documenting the reason for study suspension or termination, will be provided by the suspending or terminating party to other parties (Investigator, IRB/IEC, Sponsor and regulatory authorities). If the study is prematurely terminated or suspended, the Investigator will promptly inform the IRB/IEC and the study sites and will provide the reason(s) for the termination or suspension. Circumstances that may warrant termination or suspension include, but are not limited to:

- Determination of unexpected, significant or unacceptable risk to participants
- Demonstration of efficacy that would warrant stopping
- Insufficient compliance with study protocol requirements
- Data that are not sufficiently complete and/or evaluable
- Determination of futility

Study may resume once concerns about safety, study protocol compliance, data quality are addressed and satisfy the Sponsor and IRB/IEC.

The sponsor may decide to discontinue a specific study site under the following conditions:

- Non-compliance to GCP or study protocol
- Failure to enroll in subjects
- Unsafe or unethical practices

Clinical Protocol

A Prospective, Multi-center, Study to Evaluate the Safety and Effectiveness of REAL INTELLIGENCE™ CORI™ in unicondylar knee arthroplasty (UKA) and total knee arthroplasty (TKA) procedures

Study Number: CORI.2019.07

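### In this non-blinded study the time benchmarks and the major deviations behind the per-protocol sensitivity set may be settled as late as database lock, after the outcomes exist

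*Combined protocol and SAP*

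**What the plan says.** Section 10 gives one deadline for the SAP: "A Statistical Analysis Plan (SAP) will be written and finalized prior to database lock". Section 8.4.4 lists pre-specification among the measures against bias. It says that the primary outcome and type of analysis are already set and leaves further detail to the SAP, without a date.

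Two items are left open until then:

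- **Time benchmarks.** Section 10.4.3 compares mean Robotics System time and cutting time with literature values by t-test, with three named conclusions. It gives no values: "Standard Robotics System and cutting times will be obtained from literature and included in the SAP".
- **PP exclusions.** Section 10.2 fixes eligibility failure as a major deviation. All other criteria "will be formally classified on a case-by-case basis prior to the final study database lock".

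Section 8.1 describes a "prospective, multi-center, non-randomized, non-blinded follow-up study". The primary endpoint is the "proportion of subjects achieving post-operative leg alignment at 6 weeks post-surgery", and Section 9.1.4 has the site read the films at that visit: "Review the images to complete the appropriate eCRF for leg alignment and component alignment". Section 9.2.7 takes the times from the CORI Case Report and keeps them out of the eCRF. Section 10.1 assigns the analysis to the sponsor's own biostatistics group. No section restricts who may see outcomes before the SAP is final.

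**The concern.** Database lock is a sound deadline for a SAP when results are hidden until then. Here nothing is hidden by design. Alignment is known at 6 weeks and times are available from the day of surgery. Because the times sit outside the eCRF, database lock does not clearly govern access to them.

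A t-test against a literature value depends as much on that value as on the data, and published values may differ. A PP analysis supports the FAS result only if membership of the set does not depend on the outcome. If either choice can be made with results in view, a reader of the final report cannot tell whether it was. At stake is the credibility of the time comparisons and of the PP sensitivity analysis.

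**Working it through.** **Inputs.** Visit windows: 42 ± 14 and 365 ± 30 days (Table 9-1). Reference rate 73.4%, expected rate 92.1%, 36 evaluable and 40 enrolled knees per group (Section 11). Exact two-sided 95% interval, lower limit above 73.4% in both groups (Section 10.4.1). No SD for the times is given, so that part is in SD units.

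**The plan's own figure.** With 36 knees the smallest passing count is 32 (Clopper-Pearson lower limit 73.9%). P(X ≥ 32) is 0.021 at a true rate of 73.4% and 0.849 at 92.1%. Of the sizes checked from 30 upward, 36 is the first to reach 80% power, and 36 / 0.9 = 40. The stated sample size reproduces and is not affected by this point.

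**Timing.** The last subject's 6-week window closes on day 42 + 14 = 56. The 12-month window opens on day 365 − 30 = 335. The gap is 335 − 56 = 279 days. Most subjects' data exist far earlier, since enrolment is planned over 24 months.

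**PP leverage.** Exact lower limits when a group is one knee short of passing, before and after one misaligned knee is excluded:

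| Evaluable knees | Before | After | Change |
|---|---|---|---|
| 40 | 35/40: 73.2% | 35/39: 75.8% | fail to pass |
| 39 | 34/39: 72.6% | 34/38: 75.2% | fail to pass |
| 38 | 33/38: 71.9% | 33/37: 74.6% | fail to pass |
| 37 | 32/37: 71.2% | 32/36: 73.9% | fail to pass |
| 36 | 31/36: 70.5% | 31/35: 73.3% | fails both times |

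As an upper bound, suppose only misaligned knees are excluded, and only when that helps. At a true rate of 73.4% the chance that one group passes in the PP set is then P(X ≥ c), where c is the smallest rescuable count:

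| Exclusions allowed | n=40: c, chance | n=36: c, chance |
|---|---|---|
| 0 | 36, 0.9% | 32, 2.1% |
| up to 1 | 35, 2.7% | 32, 2.1% |
| up to 2 | 34, 6.4% | 31, 5.6% |
| up to 3 | 33, 12.9% | 30, 12.0% |

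**Benchmark leverage.** The half-width of the 95% interval for a mean is t(0.975, n−1)/√n in SD units: 2.023/√40 = 0.320 at n=40 and 2.030/√36 = 0.338 at n=36. The full width at n=40 is 2 × 0.320 = 0.64 SD. Two benchmarks further apart than that can lie on opposite sides of the same interval, one giving a longer and the other a shorter finding. A benchmark 0.3 SD above the true mean gives the shorter finding with probability 46% at n=40; at 0.5 SD above, 87%.

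This assumes that shorter means the upper limit lies below the benchmark. Section 10.4.3 prints the opposite sign. As printed, a benchmark below the lower limit would satisfy both the longer and the shorter rule.

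**The case against.** The strongest reply is that the inference that matters is already fixed. Section 10.4.1 sets the threshold, the interval, the requirement that both groups pass, and the FAS as primary. The PP set is a sensitivity analysis, the times are other endpoints, Section 5.4 says no claims are to be confirmed, and Section 10.6 has no interim analysis. All of this stands. A reader might infer from the SAP deadline that the primary comparator or primary population can follow the data; the protocol rules that out.

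A reader might also infer that the choices were in fact made with results in view. The documents do not show it. Alignment is read at site, times must be extracted from case logs, and no SAP text or date is available to check. The protocol permits a late choice and shows no more than that.

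The PP example depends on the number of evaluable knees. At the planned 36, a single exclusion rescues nothing. Because both groups must pass, a reversal in one group need not change even the overall PP conclusion, and it never changes the FAS conclusion.

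Section 8.1 adds that "The study data may be combined for analysis to meet the requirements for regulatory approval of the CORI Robotics" and refers to Section 10, which has nothing on pooling. It is tempting to prescribe a pooling method here. That would rest on two other protocols not supplied, and pooling serves a separate submission. The empty cross-reference is an editorial matter.

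Finally, Section 8.2.1 requires continuing data review, so the sponsor cannot be barred from seeing individual values. A closed deviation list could not cover unforeseen events. Both limits shape the fix.

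None of this removes the gap: two choices are open until lock, with no masking or access rule.

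**Conclusion.** The point holds for the time benchmarks and the PP exclusions, and not for the primary FAS analysis. As dated, the SAP cannot serve as the safeguard that Section 8.4.4 describes for those two items.

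One excluded knee can reverse a group's PP result at 37 to 40 evaluable knees but not at 36. The bound on a false PP pass in one group at n=40 rises from 0.9% to 2.7% with one exclusion and 12.9% with up to three. Benchmarks more than about 0.64 SD apart can reverse a time conclusion at n=40.

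These figures assume that lock follows the last 12-month visit and that the last subject treated attends it within the window, that exclusions fall only on misaligned knees (a worst case, not a forecast), and that the inequality in Section 10.4.3 is corrected. Whether literature benchmarks actually differ by 0.64 SD cannot be judged from the documents.

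**What to change.** - **Section 10.** Require the SAP, including sourced values for both time benchmarks and the major-deviation criteria, to be final before any aggregate summary of 6-week alignment or Case Report times is produced. Except routine data cleaning. If such a summary already exists, the SAP should carry its date and state what had been seen. Section 22.1.2.2 speaks of avoiding further recruitment, so recruitment may have been under way by version 6.0 and this fallback may be the one that applies.
- **Section 10.2.** Require major deviations, including unforeseen ones, to be classified from listings that omit the alignment result.
- **Section 10.4.3.** Correct the sign in the rule for a shorter time in the same revision.

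Sample size, alpha and power do not change, and there is no cost in patients or data. The SAP is written earlier and cannot be adapted as freely late in the study, and someone must prepare deviation listings without the alignment result.

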10.1 General

Smith Nephew's Global Biostatistics group will conduct the statistical analysis for this study. Unless otherwise stated, all significance tests and hypothesis testing will be two-sided, performed at the 5% significance level. Resulting p-values will be quoted and 95% two-sided confidence intervals

Clinical Protocol

A Prospective, Multi-center, Study to Evaluate the Safety and Effectiveness of REAL INTELLIGENCE™ CORI™ in unicondylar knee arthroplasty (UKA) and total knee arthroplasty (TKA) procedures

Study Number: CORI.2019.07

Version: 6.0, 15/Jan/2024

Page: 55 of 122

will be generated where appropriate. Where data summaries are specified, categorical and ordinal variables will be summarized with frequencies and percentages. Continuous variables will be summarized with the following summary statistics: the number of observations, mean, median, standard deviation, minimum and maximum values.

All statistical comparisons of data would describe the test statistic used as well as its distributional assumptions. For continuous variables, in an event of marked deviation from normality assumption, a commensurate non-parametric test would be used as an alternative thereby eliminating the possibility of violation of normality assumptions. All analyses will be performed using SAS version 9.3 (or a later version).

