11. SAMPLE SIZE JUSTIFICATION

Parratte et al.[53] looked at the effects of postoperative mechanical axis alignment on the survival of TKAs. They found that of the 398 TKAs reviewed in the paper there were 292 (73.4%) which post-operatively were defined as mechanically aligned (i.e. with a mechanical axis of $0^\circ \pm 3^\circ$).

This study is designed to demonstrate superiority in the proportion of TKAs post-operatively defined as mechanically aligned against the reference proportion of 73.4% from above.

Clinical Protocol

A Prospective, Multi-center, Study to Evaluate the Safety and Effectiveness of REAL INTELLIGENCE™ CORI™ in unicondylar knee arthroplasty (UKA) and total knee arthroplasty (TKA) procedures

Study Number: CORI.2019.07

Version: 6.0, 15/Jan/2024

Page: 60 of 122

The proportion of mechanically aligned TKAs using the NAVIO™ Surgical System from a recent analysis was estimated to be 92.1% [54]. If this assumption holds for this study, then the enrollment of 36 knees for each of the two planned study groups (i.e. the CORI Robotics UKA and CORI Robotics TKA) for a total of 72 knees will individually provide approximately 80% power to show that the lower limit of the two-sided 95% confidence interval for the proportion of mechanically aligned TKAs is greater than that obtained from literature. To account for up to a 10% attrition rate in knees enrolled, 40 knees in each group (80 knees combined, 40 UKA, 40 TKA) will be enrolled in the study.

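### Section 10.1's non-parametric switch is not disapplied for the Robotics System and cutting times, so a rank test could be set against what appears to be a literature mean (minor)

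*Combined protocol and SAP*

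**What the plan says.** Section 10.4.3 treats the times as a one-sample comparison with an external constant. The benchmarks are not yet given: "Standard Robotics System and cutting times will be obtained from literature and included in the SAP". The study averages, written with μ, "and their commensurate 95% CIs will be summarized compared to the obtained literature-specified" values (μ10 and μ20, "respectively) using the t-test"). The analyses "will be carried out separately in the CORI Robotics UKA and CORI Robotics TKA groups". Each comparison ends in one of three conclusions, according to where the 95% CI lies: significantly greater, significantly less, or comparable.

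Section 10.1 sets the general rules. Unless otherwise stated, "all significance tests and hypothesis testing will be two-sided, performed at the 5% significance level". For continuous variables, "in an event of marked deviation from normality assumption, a commensurate non-parametric test would be used as an alternative", and the section adds that this removes any risk of violating normality. It does not name the test, define a marked deviation, or list endpoints to which the rule does not apply. Section 10.4.3 neither adopts nor excludes it.

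One line of Section 10.4.3 bears on every figure below. The *significantly less* rule is printed with the upper limit **greater** than μi0. That overlaps with the *comparable* rule, under which μi0 lies between the two limits.

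**The concern.** A t-test and its CI address the mean. The usual non-parametric counterparts for one sample do not: the sign test addresses the median, and the signed-rank test addresses the pseudo-median (the centre, if the distribution is symmetric). For symmetric data these coincide with the mean and the switch is harmless. For right-skewed data they lie below the mean, so a sample whose mean exactly equals the benchmark tends to look shorter than the benchmark.

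Skewness is a common way for durations to depart from normality, so the condition that prompts the switch can be the one that makes it misleading. Normality would no longer be assumed, but the hypothesis would have changed unannounced. At stake is a formal statement that CORI times are significantly below the published figure when the means are equal.

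**Working it through.** **Inputs from the documents.** Two-sided 5% (Section 10.1), so nominal 2.5% for *less*. Separate UKA and TKA tests (Section 10.4.3). Group size from Section 11: "the enrollment of 36 knees for each of the two planned study groups" evaluable, and "40 knees in each group (80 knees combined, 40 UKA, 40 TKA) will be enrolled in the study"; 36/(1 − 0.10) = 40. That sample size belongs to the primary endpoint. The plan gives no design figure for the times, so there is none to reproduce.

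**Assumptions.** The benchmark is a mean. Times are lognormal with true mean equal to the benchmark, scaled to 1. The substitute is the signed-rank test. The *less* rule is read as upper limit < μi0.

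**Size of the parameter shift.** For a lognormal, σ² = ln(1 + CV²) and median/mean = exp(−σ²/2) = 1/√(1 + CV²). At CV 20%, 30%, 40% and 50% this is 1/√1.04 = 0.981, 1/√1.09 = 0.958, 1/√1.16 = 0.928 and 1/√1.25 = 0.894.

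**Decision rules at n=40.**
- t-test: *less* if (x̄ − μ0)/(s/√n) falls below −t(0.975, 39), which is the same as upper limit < μ0.
- Signed-rank: z = [W⁺ − n(n+1)/4]/√[n(n+1)(2n+1)/24]. Here n(n+1)/4 = 410 and the variance is 40·41·81/24 = 5,535 (SD 74.4). *Less* if z < −1.96.
- Two-stage: signed-rank if Shapiro-Wilk p is below a cut-off, otherwise t. The cut-off is an assumption, as the plan defines none.

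**Rate of *significantly less* at equal means, n=40.** Ranges cover separate runs of 4,000 samples where several were made. The 95% simulation error near 10% is 1.96·√(0.10·0.90/4,000) = 0.9 points.

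| | CV 20% | CV 30% | CV 40% | CV 50% |
|---|---|---|---|---|
| Signed-rank always | 5.1% | 6.7–7.0% | 8.5–10.0% | 11.2–12.8% |
| t-test always | 3.4% | 3.8–3.9% | 4.2–4.7% | 4.6–5.5% |
| Switch if p<0.05 | – | 6.1% | 9.0% | 10.8% |
| Switch if p<0.001 | – | 4.7–4.9% | 6.2–6.9% | 9.0–10.2% |

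The switch occurs in about 46%, 66–68% and 82% of samples with the p<0.05 trigger, and in 11%, 24% and 39% with p<0.001 (CV 30%, 40%, 50%). A check with 20,000 samples per setting gave two-stage rates of 6.1%, 8.9% and 11.8% (p<0.05) and 4.7%, 7.0% and 9.6% (p<0.001). Hence about 5–12% overall.

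**Controls and reversals (n=40).**
- Normal data: signed-rank 2.5%. Symmetric heavy-tailed t(3) data: 2.4%. The excess comes from skewness, not from non-normality as such.
- Gamma data, shapes 4 and 2: signed-rank 8.1% and 11.9%, t-test 4.1% and 4.7%. The result is not peculiar to the lognormal.
- Left skew (reflected gamma, shape 2): signed-rank gives *less* 0.3% and *greater* 11.8%.
- Benchmark a median (lognormal, log-SD 0.5): the t-test gives *greater* in 22.5% and signed-rank in 9.6%; the sign test gives 1.9% on each side.

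**Mean-based alternatives.** At CV 30%, 40% and 50%, the rate of *less* was 3.4%, 4.0% and 4.0% for a BCa bootstrap interval (2,000 runs) and 3.0%, 3.6% and 3.1% for a Cox-type lognormal-mean interval. The latter depends on its model: with gamma shape 2 data it gave 0.6%.

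**The case against.** The specific rule can be read as governing the general one. Section 10.4.3 names the t-test and ties each conclusion to the CI for the mean; Section 10.1 replaces a test and does not say that this CI rule lapses. The word commensurate could also cover a bootstrap interval for the mean, which is itself non-parametric. Section 10 is a summary of a SAP to be finalised before database lock, and Section 10.1 promises that each comparison will describe its test statistic and distributional assumptions, so the SAP may settle all this. Section 10.1 also has the mean and median reported together, so readers could see skew. Finally, the times are exploratory endpoints, and Section 5.4 says no claims are to be confirmed.

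Most of this stands, and it limits the point to a minor one. It does not remove it: the switch is worded for continuous variables generally, the times are continuous, and neither section says which rule prevails.

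A reader might go further and infer that the plan will apply a rank test to the times, so that CORI will be declared faster too often, in the sponsor's favour. The documents do not support that. The rank test is not named. That the benchmark is a mean is inferred from the averages and the μ notation. The direction depends on right skew, for which the documents give no data.

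**Conclusion.** The point holds as an unresolved conflict between Sections 10.1 and 10.4.3 that can change the tested parameter. It is minor.

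If the benchmark is a mean, the times are right-skewed and the signed-rank test is used, the false *less* rate is about 5% at CV 20% and 7–13% at CV 30–50%, against 2.5% nominal. Not all of the excess is due to the switch, because the t-test is itself somewhat liberal here. In one paired run the switch added 6.8 − 3.8 = 3.0, 9.6 − 4.4 = 5.2 and 12.8 − 5.5 = 7.3 points at CV 30%, 40% and 50%. With the strict trigger in the same run it added 4.7 − 3.8 = 0.9, 6.9 − 4.4 = 2.5 and 10.2 − 5.5 = 4.7 points.

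The primary result, which rests on exact binomial intervals, is unaffected. The printed inequality in the *less* rule is a separate error in the same text and does not depend on any of these assumptions.

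**What to change.** In Section 10.4.3 and the SAP:

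1. State that the parameter is the mean time and that the Section 10.1 switch does not apply to the Robotics System and cutting times.
2. If the times are skewed, base the conclusion on a mean-based interval named in advance. BCa bootstrap is the safer default; a lognormal-mean interval suits times that are close to lognormal.
3. Record whether each literature benchmark is a mean or a median. If it is a median, restate the hypothesis for the median and use a method for the median, such as the sign test or its interval. The signed-rank test is not suitable for that under skew.
4. Correct the *significantly less* rule to upper limit < μi0, so that the three conclusions are mutually exclusive.

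The cost is a few sentences and a few lines of code, with no new data and no change to the sample size. It should be settled before database lock, when the SAP is due to be final.
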